### 3.1.3 Extension Phase

Subjects who do not demonstrate complete metabolic response at the end of the 1 week end-of-study pharmacodynamic period (see section 3.4) following 24 weeks of treatment or at any time during the follow-up period will be offered the opportunity to resume study drug at the maximum tolerated dose if they experienced normalization of blood phosphate levels while on BGJ398. They will be allowed to continue until either study closure, patient withdrawal, or, if in the judgement of the investigator, the adverse event profile of the subject outweighs the benefit. Subjects will continue to be monitored monthly for efficacy and safety. This will include monthly telephone follow-up to assess adverse events, monthly laboratory assessments and outpatient NIH visits at a minimum of every three months, to include an ophthalmologic examination.

*Abbreviated Title: BGJ398 in TIO*  
*Version Date: 21MAY2019*

### **3.2 DRUG ADMINISTRATION**

BGJ398 will be dispensed at the start of each 28-day cycle. Patients will self-administer BGJ398 at home after the initial dose(s) are given during the inpatient period. All patients must return their bottle(s) of BGJ398 at the appropriate scheduled visit. Study site staff will monitor subject compliance assessed by the capsule count. Subjects will be instructed to notify study site personnel of any missed doses.

The following general guidelines should be followed for BGJ398 administration:

- Patients should be instructed to take the daily dose of BGJ398 in the morning, at approximately the same time each day ( $24 \pm 2$  hr interval).
- BGJ398 should be administered in the fasted state, at least 1 hour before or 2 hours after a meal.
- BGJ398 should be taken with a large glass of water (~250 mL) and consumed over as short a time as possible. Patients should be instructed to swallow the correct number of 25 mg or 100 mg capsules comprising the appropriate dose whole and not chewed, crushed, dissolved or divided.
- If the patient forgets to take the scheduled dose in the morning, he/she should not take the dose more than 2 hours after the usual time. If the time extends 2 hours or more, the dose should not be taken (missed). Any doses that are missed should be skipped altogether and should not be replaced or made up at the next scheduled dosing. The scheduled dose should be taken the next day.
- If vomiting occurs following the dosing of study drug, re-dosing is not permitted that same day. Dosing should resume the next day. This event needs to be noted appropriately.
- BGJ398 is characterized by pH-dependent solubility, and therefore, medicinal products that alter the pH of the upper gastro-intestinal tract may alter the solubility of both compounds, and limit bioavailability. These agents include, but are not limited to, proton-pump inhibitors (e.g., omeprazole), H2-antagonists (e.g., ranitidine) and antacids. Therefore, BGJ398 should be dosed at least 2 hours before or 10 hours after dosing with a gastric protection agent.
- Patients must avoid consuming Seville (blood) oranges or juice, grapefruit, grapefruit juice, grapefruit hybrids, or pomelos from 7 days prior to the first dose of study medication through the end of study participation. This is due to a potential CYP3A4 interaction with study medication. Normal oranges and orange juice are allowed.

### **3.3 DOSE MODIFICATIONS**

For patients who do not tolerate the protocol-specified dosing schedule, dose adjustments are permitted to allow the patient to continue the study treatment. The following guidelines need to be applied:

- These changes must be recorded in the patient's medical records and eCRF.
- All dose modifications should be based on the worst preceding toxicity.

*Abbreviated Title: BGJ398 in TIO*

*Version Date: 21MAY2019*

- Following resolution of toxicity to baseline or  $\leq$  grade 1, treatment is resumed at lower dose of study drug as per Table 3.3.1. If treatment is resumed at the lower dose of study drug, and the same toxicity recurs with the same or worse severity, the patient must discontinue study treatment.

Table 3.3.1 Dose reduction table:

BGJ398 dose level	BGJ398 dose
Starting level (0)	75 mg po once daily
Dose level-1	50 mg po once daily
Dose level-2	25 mg po once daily

### 3.4 END OF STUDY PHARMACODYNAMICS:

After the last dose is administered (24-week timepoint), the subject will be seen at the NIH and following labs will be done daily ( $\pm$  1 day) for up to 7 draws to evaluate for end-of-study pharmacodynamics.

- Blood FGF23
- Blood 1, 25 (OH)2-Vitamin D
- Blood Phosphorous, Calcium, and Creatinine
- Blood PTH
- Urine Calcium, Creatinine, and Phosphorous.

### 3.5 QUESTIONNAIRE

#### **RAND® Medical Outcomes Short Form Survey Instrument (SF-36) Version 1.0**

RAND Medical Outcomes Short Form Survey Instrument (SF-36) Version 1.0 will be used as a secondary outcome measure to determine effects of BGJ398 on Health-Related Quality of Life (HRQOL) over the duration of the study. The RAND® 36-Item Health Survey is a generic validated instrument used to measure (HRQOL) parameters of physical and mental health across age, disease, and treatment groups in individuals 18 years and older. The questionnaire is a multi-purpose self-reported health assessment tool composed of 36 questions in eight different domains that examine aspects of physical and mental health from the patient's point of view. This short questionnaire will be administered in paper or electronic form and completed by the patients at baseline and then monthly for the duration of the study. The average duration of time for completion of the questionnaire is 5-10 minutes. Completed paper versions of the survey will be coded with the subject number and kept in a binder in a locked office. Data collected by means of an electronic tablet

*Abbreviated Title: BGJ398 in TIO*  
*Version Date: 21MAY2019*

	Prescreen	Screen	V0	V 1	V 2	V 3	V 4	V 5	V 6	V 7	V 8	V 9	V 10	V11	V12	V13	V 14	V 15	V 16	V1 7	V 18
Target Date (weeks)		(-)0-6	0	2	4	6	8	10	12	14	16	18	20	22	24	26	28	30	32	34	36
Visit Window (days)		±4	± 4	± 4	± 4	± 4	± 4	± 4	± 4	± 4	± 4	± 4	± 4	± 4	± 4	± 4	± 4	± 4	± 4	± 4	± 4
FGF23 (Mayo)		X	X	X	X	X	X	X	X	X	X	X	X	X	X		X		X		X
BGJ398 - PK Testing			X		X		X														
Urine testing																					
Urine every 2 hours (± 20 minutes) for Pi and Creatinine			X																		
Spot urine Pi, Ca, creatinine				X		X		X		X		X		X	X §						
Urine Pregnancy test (if indicated)		X	X		X		X		X		X		X		X		X		X		X
Urinalysis		X	X		X		X		X		X		X		X		X		X		X
24-hour Ca, Pi, creatinine		X	X		X		X		X		X		X		X		X		X		X
Consults and imaging testing																					
Ophthalmology evaluation (monthly while on BGJ398)			X		X		X		X		X		X		X						X
Nuclear medicine studies (if not done in last 6 mos – repeated at 24 weeks in those with identified tumors)		X													X						
Electrocardiogram (every 4-12 weeks as indicated)		X																			
Echocardiography			X				X								X						
US kidney			X												X						

^ At the inpatient visit (during the first drug administration), blood and urine will be collected every 2 hours (± 20 minutes) for 24 hours to measure phosphorous and TRP and every 4 hours to measure FGF23, intact PTH, ionized calcium, 1, 25 (OH)2 vitamin D.

^^ DASH: The Disabilities of Arm Shoulder and Hand Outcome Measurement

# BGJ398 is administered during the first in patient visit. The patient will be supplied with the drug every 4 weeks for total of 6 months. The patient will be started on 75 mg dose and the dosage changes will be made based on the adverse events and response as described in the protocol.

\*Outside labs may be done at NIH or at outside lab based on patient convenience.

§ V12 (24-weeks) may be done as an inpatient or outpatient visit based on patient convenience. Labs are drawn at the NIH daily (±1 day) for total of 7 lab draws for blood FGF23, 1- 25 (OH)2-Vitamin D, Phosphorous, Calcium, Creatinine and iPTH, Urine Calcium, Creatinine, and Phosphorous.

*Abbreviated Title: BGJ398 in TIO*

*Version Date: 21MAY2019*

### **3.7 SURGICAL GUIDELINES: NOT APPLICABLE**

### **3.8 RADIATION THERAPY GUIDELINES: NOT APPLICABLE**

### **3.9 COMPENSATION: NOT APPLICABLE**

### **3.10 CRITERIA FOR REMOVAL FROM PROTOCOL THERAPY AND OFF STUDY CRITERIA**

#### **3.10.1 Criteria for permanent removal from protocol therapy**

Subjects will be informed that they may choose to withdraw or the investigator may remove them from BGJ398 if it is in their best interest or if the subjects are unable to complete the required assessments and/or treatment. Voluntary withdrawal from the protocol is always an option for research participants.

The following conditions will require the permanent withdrawal of a subject from the BGJ398 therapy:

- Pregnancy
- Decline in calculated GFR to  $\leq 25$  mL/min/1.73 m^2 or decline in calculated GFR by 25 mL/min/1.73m^2 without clear etiology that persists on three monthly measurements (measured at the NIH or the subject's local laboratory).
- CTCAE  $\geq$  Grade 4 abnormalities in hepatic transaminases (ALT and AST)
- Treatment failure as defined by a blood phosphorus level below the lower limit of normal while taking the maximum tolerated dose of BGJ398 on two consecutive cycles.
- Investigator judgment based on subject's best medical interest

Subjects who require permanent discontinuation of BGJ398 therapy due to an adverse event will continue to be followed in the study until the toxicity has resolved or up to 30 days after study drug discontinuation. Pregnancies will be recorded from the time written informed consent is obtained until the subject is withdrawn from the study. Subjects who become pregnant during the study will be taken off BGJ398 and will be followed (with the subject's permission) until a pregnancy outcome is reached. The subjects will be referred to a physician outside of NIH for care. If the pregnancy results in anything other than a normal birth or elective abortion of a healthy fetus, it will be reported as an SAE. At the end of the pregnancy follow-up period, the subjects will be withdrawn from the trial.

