13. Recent ( $\leq$ 3 months) transient ischemic attack or stroke
14. Patients under age 21 will have a bone age assessed as part of their clinically indicated skeletal survey under 01-D-0184 and will not be offered enrollment if their growth plates are open.
15. Pregnant or nursing (lactating) women, where pregnancy is defined as the state of a female after conception and until the termination of gestation, confirmed by a positive hCG laboratory test
16. Women of child-bearing potential, defined as all women physiologically capable of becoming pregnant, unless they are using highly effective methods of contraception during dosing and for 3 months following the discontinuation of study treatment. Highly effective contraception methods include:
- Total abstinence (when this is in line with the preferred and usual lifestyle of the subject. Periodic abstinence (e.g., calendar, ovulation, symptothermal, post-ovulation methods) and withdrawal are not acceptable methods of contraception
  - Female sterilization (have had surgical bilateral oophorectomy with or without hysterectomy) or tubal ligation at least six weeks before taking study treatment. In case of oophorectomy alone, only when the reproductive status of the woman has been confirmed by follow up hormone level assessment
  - Male sterilization (at least 6 months prior to screening). For female subjects on the study the vasectomized male partner should be the sole partner for that subject.
  - Combination of the following (a+b or a+c, or b+c):
    - a. Use of oral, injected or implanted hormonal methods of contraception or other forms of hormonal contraception that have comparable efficacy (failure rate <1%), for example hormone vaginal ring or transdermal hormone contraception
    - b. Placement of an intrauterine device (IUD) or intrauterine system (IUS)
    - c. Barrier methods of contraception: Condom or Occlusive cap (diaphragm or cervical/vault caps) with spermicidal foam/gel/film/cream/vaginal suppository

Post-menopausal women are allowed to participate in this study. Women are considered post-menopausal and not of child-bearing potential if they have had 12 months of natural (spontaneous) amenorrhea or 6 months of spontaneous amenorrhea with serum FSH >40 mIU/ml or 6 weeks postsurgical bilateral oophorectomy with or without hysterectomy.

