Sexually active males unless they use a condom during intercourse while taking drug and for 3 months after the last dose of the study drug and should not father a child in this period. A condom is required to be used also by vasectomized men in order to prevent delivery of the drug via seminal fluid.

Patients with TIO who are currently taking BGJ398 or have been treated with BGJ398 in the past are eligible to participate in this study, provided that they discontinue BGJ398 for 2 weeks prior to the baseline visit.

*Abbreviated Title: BGJ398 in TIO*

*Version Date: 21MAY2019*

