### **3 STUDY IMPLEMENTATION**

#### **3.1 STUDY DESIGN**

Calcitriol (half-life is 5-8 hour) and phosphorous will be withheld for 3 days prior to the initiation of BGJ398 to allow for washout.

After initiation of study drug, subject will complete 24 weeks of BGJ398 with escalation/de-escalation of drug as described in Sections 3.1.2 and 3.3. Patients will return to the NIH every 4 weeks while on BGJ398 for an outpatient visit and labs per the schedule of events. Between monthly NIH visits, labs will be obtained per the schedule of events at the patients' local laboratories and results will be forwarded to the study team for review. In addition, any patient taking a concomitant medication associated with prolonged QT will obtain an EKG as an outpatient within 7-10 days after an increase in BGJ398 or the relevant concomitant medication. At the end of 24th week of BGJ398 treatment, subjects will be admitted as inpatients at the NIH for detailed laboratory and imaging evaluation as described in schedule of events. At the completion of the 24 weeks of treatment, patients who appear to have had a complete metabolic response will be evaluated at the NIH every 4 weeks for 3 additional visits. Complete metabolic response will be defined as normalization of blood phosphate and FGF23 levels after withdrawal of study drug. Local labs will be obtained in between NIH visits as clinically indicated on an as-needed basis. Subjects who have normal phosphate levels while on BGJ398 but have not had a complete metabolic response at the end of the 24 weeks of study drug may be considered for drug continuation in the extension phase, described in 3.1.3. Those who have not responded, have experienced significant side effects, or do not want to continue in the extension phase, will be terminated from the study and referred for other treatment.

During the active drug study period, subjects will not receive calcitriol and phosphorous supplements. However, subjects may be placed on calcitriol and phosphorous while in the post-BGJ398 drug monitoring phase or during dose interruptions, as clinically indicated. During the post-drug monitoring period calcitriol and phosphorous will be re-started on individual basis as clinically indicated (muscle weakness, bone pain, hypophosphatemia).

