### **7.5.5 Reporting procedures**

The investigator must complete the FDA MedWatch 3500a form and QED SAE report form in English, assess the relationship to study treatment and send the initial completed MedWatch form and QED SAE Report Form to Chiltern Pharmacovigilance via fax or email within 24 hours of becoming aware of the SAE. The original FDA MedWatch form and QED SAE report form must be kept with the case report forms at the study site.

Follow-up information should describe whether the event has resolved or continues, if and how it was treated, and whether the patient continued or discontinued study participation. The MedWatch form and QED SAE report form must be retained. Pregnancies

Any pregnancy that occurs during study participation should be reported. To ensure patient safety Within 24 hours of the site becoming aware of a pregnancy in either a study subject or the partner of a study subject, the Investigator is required to notify QED by completing the Pregnancy Notification Report and sending to Chiltern Pharmacovigilance via email (or) fax. The pregnancy should be followed up to determine outcome, including spontaneous or voluntary termination, details of birth, and the presence or absence of any birth defects, congenital abnormalities or maternal and newborn complications using the Pregnancy Follow-up Report form.

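### Pregnancies must be recorded only until a patient leaves the study, which by some exit routes is well before the protocol's 3-month post-dose contraception period ends

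*Combined protocol and SAP*

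**What the plan says.** **Contraception period.** Section 2.1.2 excludes women of child-bearing potential unless they are "using highly effective methods of contraception during dosing and for 3 months following the discontinuation of study treatment". Sexually active men must use condoms during treatment and "for 3 months after the last dose of the study drug and should not father a child in this period".

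**Recording and reporting period.** Section 3.10.1 states: "Pregnancies will be recorded from the time written informed consent is obtained until the subject is withdrawn from the study". Section 7.5.5 states: "Any pregnancy that occurs during study participation should be reported". The 24-hour notification duty that follows covers "a pregnancy in either a study subject or the partner of a study subject", but it sits under the same limit of study participation.

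**When patients leave.** Under 3.1, after 24 weeks of drug, those who have not responded, have had significant side effects or decline the extension "will be terminated from the study and referred for other treatment". Section 3.4 describes up to 7 roughly daily draws after the last dose. Section 6.3.4 judges complete metabolic response at the end of that week and follows complete responders for a further 11 weeks (± 2 weeks). Under 3.10.1, patients permanently stopped for an adverse event are followed until the toxicity clears, to a limit of 30 days after stopping. Section 3.1.3 says when extension treatment ends but is silent on follow-up afterwards.

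**Late serious events.** Section 7.1 has serious adverse events arising more than 30 days after the last dose recorded and reported if they are judged at least possibly related. It lists congenital anomaly among serious outcomes.

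**The concern.** By requiring contraception for 3 months after the last dose, the protocol defines its own period of reproductive risk. The recording rule is tied to study status instead, and study status after week 24 depends on response, tolerance and willingness to enter the extension. Drug exposure does not depend on those things in the same way. Two patients with the same exposure can therefore have very different coverage.

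The schedule of events shows the practical side. Urine pregnancy tests are planned at weeks 28, 32 and 36, but under 3.1 and 6.3.4 only patients kept in off-drug follow-up attend those visits.

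What is at stake is safety information about pregnancies that begin, or first become known, after exit but within the 3 months. Section 3.10.1 follows a pregnancy to its outcome, and treats most abnormal outcomes as serious adverse events, only for subjects who become pregnant during the study. A pregnancy after exit does not start that process. Uncomplicated outcomes would also be missing, so any abnormal outcome that did reach the site would have no denominator.

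**Working it through.** No sample size, power or error rate is involved. The check compares two time windows.

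**Inputs**
- *W*, post-dose contraception period: 3 months (2.1.2). The documents give no day count; I assume 90 to 92 days, or about 13 weeks.
- *F*, time on study after the last dose, by exit route:
  - no complete response and no extension: about 7 days, inferred from 3.1, 3.4 and 6.3.4 together;
  - permanently stopped for an adverse event: at most 30 days (3.10.1);
  - complete responder: 1 week + 11 weeks = 12 weeks = 84 days, or 70 to 98 days with the ± 2 week allowance (3.4, 6.3.4);
  - after the extension: none stated (3.1.3).

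**Timeline check.** 24 + 1 + 11 = week 36. This agrees with the last scheduled visit (V18, week 36) and with the 12-week follow-up period in 8.3.

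**Formula.** Days not covered by the recording rule = *W* − *F*.

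| Exit route | *F* (days) | *W* − *F* (days) |
|---|---|---|
| Leaves after week 24, no extension | about 7 | 90 − 7 = 83 to 92 − 7 = 85, about 92% of *W* |
| Stopped for an adverse event | at most 30 | at least 90 − 30 = 60 to 92 − 30 = 62 |
| Complete responder, nominal | 84 | 90 − 84 = 6 to 92 − 84 = 8 |
| Complete responder, shortest follow-up | 70 | 90 − 70 = 20 to 92 − 70 = 22 |
| Complete responder, longest follow-up | 98 | none; 98 − 92 = 6 to 98 − 90 = 8 beyond *W* |
| After the extension | not stated | up to the whole of *W* |

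In weeks, the first row is 13 − 1 = 12 of 13.

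**Sensitivity to the length of 3 months.** The précis calls the off-drug follow-up 3 months, and the schedule makes it 12 weeks. Reading *W* as 84 days gives 84 − 7 = 77 days (92%), 84 − 30 = 54 days and 84 − 84 = 0 days for the first three rows. The pattern is unchanged: large gaps for early leavers and essentially none for complete responders.

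**Search for a closing provision.** Nothing in 2.1.2, 3.1, 3.1.3, 3.10 or 7.5.5 requires a pregnancy test, contact or pregnancy record after a patient has left the study.

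**The case against.** **Section 7.1 is a real safety net.** A reader might infer that a birth defect after exit would go uncollected. The documents do not support that. The late-event rule in 7.1 has no upper time limit and does not depend on study status. Congenital anomaly is a listed serious outcome, and 7.5.4 requires every serious adverse event to reach the manufacturer within 24 hours of the site learning of it. A late anomaly judged at least possibly related is therefore reportable once known. What remains is narrower: nothing prompts the site to ask, and the pregnancy itself need not be recorded.

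**The 1-week exit is not stated.** No section gives an off-study day for patients without a complete response. The précis describes 3 months of off-drug follow-up without limiting it to responders. Section 6.3.3.3 sets best overall response at 9 months, including partial response and progression. The off-study list has no non-response criterion and does include completion of follow-up. This stands as a caution on the figure. Section 3.1 is the more specific text, however: it gives the three extra visits to apparent complete responders and terminates the others described there.

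**Not every patient without a complete response is affected at week 25.** Those whose phosphate normalised on drug may enter the extension and stay on study, and those who lose response during follow-up leave later. It would also be too strong to say that extension patients leave the day they stop drug: 3.1.3 is silent, and the 30-day adverse-event rule in 3.10.1 is not confined to the main phase.

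**Complete responders.** The nominal shortfall of about a week lies within the ± 2 week allowance and is not a defect on its own.

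**Scale and unseen material.** The trial has 10 patients and requires contraception; the number of women of child-bearing potential is not given. No endpoint or analysis is affected. The consent pages and the content of the patient instructions (Appendix 3) are not available, so patients may be told to report later pregnancies. The point is therefore limited to what 3.10.1 and 7.5.5 require.

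**Conclusion.** The inconsistency is real and of modest weight. Followed exactly, the recording and reporting rules stop short of the protocol's own 3-month period for patients who leave early: about 12 of 13 weeks for those leaving after week 24 without a complete response or the extension, at least about 60 days for those stopped for an adverse event and followed for up to 30 days, and an undefined amount after the extension. Complete responders are approximately covered.

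These figures rest on taking 3 months as 90 to 92 days and on the inferred exit at about day 7. The conclusion does not depend on either exact value, because any exit before 3 months leaves a gap. Few pregnancies are to be expected among 10 patients, so the case for change is that the safety record is incomplete for a period the protocol itself marks as relevant and that closing it is cheap. It is not that a detectable signal would be lost.

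**What to change.** Reconcile 3.10.1 and 7.5.5 with 2.1.2. State that pregnancies in patients and in partners are recorded and reported from consent to the end of the post-dose contraception period given in 2.1.2, including for patients who have already left the study. Make this subject to the permission of the patient, and of the partner where the partner is pregnant, and exclude collection after withdrawal of consent. Section 3.10.1 already makes pregnancy follow-up conditional on the subject's permission, so this extends an existing principle.

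Add one telephone contact at the end of that period for patients who left earlier and agree to it. State in 3.1.3 that the same applies after the last extension dose. It would also help to give the off-study day for patients who leave after week 24, so that the exit point need not be inferred.

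The cost is protocol and consent wording and at most one call per early leaver in a 10-patient trial. No dose, contraception rule or treatment decision changes.
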